## 20.0 Data Management and Confidentiality

20.1 The captured CEUS images will be evaluated by a single Children's Mercy Hospital pediatric radiologist to determine and establish a pattern compared to the standard gray scale ultrasound report. This radiologist will be blinded to the final reads from the gray scale reports. For the children who meet the criteria of appendicitis, they will be followed post-operatively to confirm and correlate the intra-operative findings with the gray scale read.

Descriptive analysis of demographics and patient-level data will be performed using STATA. Direct comparisons will be made with parametric or nonparametric measures depending on the distribution of the data.

- 20.2 This study will be made up of a convenience sampling of children presenting to the CMH Adele Hall emergency department with concerns for appendicitis. Enrollment will consist of up to 250 participants.
- 20.3 All data will be entered into a REDCap database that is accessible only to researchers named on the study. Data will be stored on the CMH secure network. The list of chart identifiers which meet inclusion criteria along with dates of birth will be maintained separately from data that will be used for analysis. Each chart will be reviewed by research staff and data entered directly into the research records. The researchers alone will have full access to the data; we will assign a study ID to the medical records in order that we can reference our information during the course of our research. A master list linking Study ID to MRN, Name and other identifiers will be kept separately from the study data, and accessible only to the study team.
- 20.4 N/A
- 20.5 All data will be entered into a REDCap database that is accessible only to researchers named on the study. Data will be stored on the CMH secure network. The list of chart identifiers which meet inclusion criteria along with dates of birth will be maintained separately from data that will be used for analysis. Each chart will be reviewed by research staff and data entered directly into the research records. The researchers alone will have full access to the data; we will assign a study ID to the medical records in order that we can reference our information during the course of our research. A master list linking Study ID to MRN and other identifiers will be kept separately from the study data, and accessible only to the study team.
- 20.6 All data will be entered into a REDCap database that is accessible only to researchers named on the study. Data will be stored on the CMH secure network. The list of chart identifiers which meet inclusion criteria along with dates of birth will be maintained separately from data that will be used for analysis. Each chart will be reviewed by research staff and data entered directly into the research records. The researchers alone will have full access to the data; we will assign a study ID to the medical records in order that we can reference our information during the course of our research. A master list linking Study ID to MRN and other identifiers will be kept separately from the study data, and accessible only to the study team.

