## 4.0 Study Endpoints

4.1 The primary endpoint is the proportion of patients for whom the appendix is enhanced by CEUS when using the same diagnostic criteria as gray scale ultrasound. Lumason will be considered effective if the sensitivity of grayscale ultrasound is enhanced in more than 50% of images as determined by the blinded interpreting pediatric radiologist.

Secondary endpoints include:

- Utility of CEUS in making a definitive diagnosis of acute appendicitis
- Utility of CEUS in decreasing rates of CT scan utilization
- Negative appendectomy rates

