5.3 N/A

## 6.0 Procedures Involved

- 6.1 This will be a single-center non-randomized trial that will add to our institution's current diagnostic algorithm one CEUS to subjects whom are clinically suspicious for acute appendicitis. Currently, a gray-scale abdominal ultrasound is performed to help establish the diagnosis. When the results of the gray-scale abdominal ultrasound are inconclusive, the treating physician may choose to refer the patient for a CT scan in order to establish a definitive diagnosis. Our study does not look to alter that process.
- 6.2 For those who consent to study participation, we propose obtaining a CEUS after the initial gray-scale ultrasound. Once the initial ultrasound is complete, the contrast Lumason® (sulfur hexafluoride lipid type-A microspheres) will be administered through an already existing IV catheter by an MD, RN or a radiology technologist trained and certified to administer the Lumason® contrast agent, and

an abdominal scan will be completed. The patient will then continue with standard of care treatment per his treating physician. The CEUS image will be read at a future time by a CMH radiologist blinded to the results of the gray scale ultrasound and CT if one was obtained as these will be used for comparison.

6.3

- Lumason will be administered by radiology personnel (radiologist, US technologist, or Sedation RN). Subjects will be monitored during the entirety of the procedure. Once the study procedure has been completed, patients will continue to go through the standard of care process and return to the ED (Emergency Department) or floor while they await the results of their gray-scale ultrasound and CT, if one was obtained. ED/ floor staff will continue to monitor patients for any adverse events.
- Lumason (sulfur hexafluoride lipid-type A microspheres) is the investigational product. The recommended dose of Lumason for children is 0.03 mL/kg up to a maximum dose of 2.4mL injected into a peripheral intravenous catheter. See individualization of dose below.

1. Follow the Lumason injection with a flush of 5 ml of 0.9% Sodium Chloride Injection, USP.
2. The maximum total dose for children as listed in the package insert should not exceed 2.4 mL in any 10-minute period. For this study, over any 10-minute period we intend to administer the approved dose of 0.03 mL/kg up to a maximum of 2.4 mL.

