3. The maximum total dose for children as listed in the package insert should not exceed 4.8 mL in any one patient during the full time on study. In this study, we intend to administer a total dose in any one patient during the full time on study of 0.06 mL/kg with a maximal dose of 4.8 mL.

6.4 Data extracted from the electronic medical record will be entered into a secure REDCap database and stored in a password protected file on the CMH network. A master list containing only the assigned study ID and linking MRN will be kept in a separate REDCap instrument. All electronic files will be kept on the secure password-protected computers of the research staff and principal investigator.

Data points to be collected include the following: demographics, findings on radiology imaging (US, CEUS, and CT if applicable),

pathology, intraoperative findings, other/ comments. Reports of headache, nausea, altered taste, injection site reaction, feeling hot/ flushed, chest pain, or dizziness will also be recorded.

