26.2 N/A

26.3 N/A

## **27.0 Setting**

27.1

- Study team members (specifically surgery fellows and attending's) will identify patients presenting to the CMH Adele Hall Emergency Department with concerns of appendicitis, and will approach patients/parents to recruit for the study.
- Ultrasounds will be performed in the Radiology department at CMH Adele Hall. Data will be collected by study team members at CMH Adele Hall Emergency, Radiology and Surgery departments.

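### Section 20.1 checks the gray-scale read against the surgeon's intra-operative findings and gives no role to the pathology already collected; the CEUS read is checked against neither

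*Protocol*

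**What the plan says.** Section 20.1 is the only place in the protocol that ties an imaging read to what is found at surgery. The group is "For the children who meet the criteria of appendicitis", and the check is that "they will be followed post-operatively to confirm and correlate the intra-operative findings with the gray scale read". The criteria are not spelled out there.

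Section 6.4 lists the data to be extracted, among them "pathology, intraoperative findings, other/ comments". Pathology and operative findings are thus two separate items, and both are collected. No section gives pathology a part in judging either read.

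On who knows what, 6.1 says of standard care: "Currently, a gray-scale abdominal ultrasound is performed to help establish the diagnosis". Section 6.1 adds that the study does not seek to change that pathway. Section 27.1 says "Study team members (specifically surgery fellows and attending's) will identify patients", so surgeons belong to the study team. The blinding that is described concerns the CEUS reader: "This radiologist will be blinded to the final reads from the gray scale reports". Section 6.2 extends that reader's blinding to CT and names gray scale and CT as the comparators for CEUS.

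The success criterion in 4.1 is "Lumason will be considered effective if the sensitivity of grayscale ultrasound is enhanced in more than 50% of images", as judged by the blinded radiologist. The secondary endpoints in 4.1 include the use of CEUS in reaching a definitive diagnosis and the negative appendectomy rate. Neither is given a reference standard.

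**The concern.** A reference standard should be the best evidence available, and it should be judged without knowledge of the test it is used to assess. The operative impression is doubtful on both counts. It is a visual judgement, while a tissue result on the same appendix is already being recorded. It also comes from a clinician who has probably seen the gray-scale result. If that knowledge sways borderline calls, gray scale is partly checked against itself and the correlation comes out too high.

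Three things are at stake. The reported accuracy of gray scale, the existing test, may be wrong. CEUS, the test under study, has no stated check against surgical truth at all, so a statement about definitive diagnosis has no common yardstick for the two reads. And the negative appendectomy rate, which is not defined, could be taken from a different source than the one used in 20.1.

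**Working it through.** **Step 1: the texts side by side.**

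| Question | Where | Answer |
|---|---|---|
| Which operative evidence is compared with a read? | 20.1 | Intra-operative findings |
| Which read is compared? | 20.1 | Gray scale only |
| Is pathology collected? | 6.4 | Yes, as a separate item |
| Is pathology used as a reference? | No section | Not stated |
| Does gray scale inform care? | 6.1 | Yes, it is part of the standard work-up |
| Is the surgeon blinded to it? | No section | Not stated |
| Is the CEUS reader blinded? | 6.2, 20.1 | Yes |
| Does the primary endpoint use an operative reference? | 4.1 | No |

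The surgeon's knowledge of the read is therefore an inference from standard care and from the absence of any surgeon blinding. It is not stated.

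**Step 2: is there a figure to reproduce?** No. The protocol states no expected sensitivity or specificity, no surgeon-pathology agreement and no sample-size calculation that depends on the reference.

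**Step 3: illustration. Every input is assumed.** Among operated children, let p be the share with appendicitis (90 or 95%). Let gray-scale sensitivity and specificity be 80%/50% or 90%/70%. As shares of all operated children:

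- TP = p × sens, FN = p × (1 − sens)
- FP = (1 − p) × (1 − spec), TN = (1 − p) × spec

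Let q (5 to 20%) be the share of children in whom the surgeon's call follows the gray-scale read rather than the true state. Only discordant children change cell:

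- TP' = TP + q·FP, FP' = (1 − q)·FP
- FN' = (1 − q)·FN, TN' = TN + q·FN

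Example with p = 90%, 80%/50%, q = 20%. The true cells are TP 0.72, FN 0.18, FP 0.05, TN 0.05. They become TP' 0.73, FN' 0.144, FP' 0.04, TN' 0.086.

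- Sensitivity: 0.73/0.874 = 83.5%
- Specificity: 0.086/0.126 = 68.3%
- PPV: 0.73/0.77 = 94.8%
- Agreement: 0.73 + 0.086 = 81.6%

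True value → apparent value at q = 20%:

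| p | Sensitivity | Specificity | PPV | Agreement |
|---|---|---|---|---|
| 90% | 80.0 → 83.5 | 50.0 → 68.3 | 93.5 → 94.8 | 77.0 → 81.6 |
| 90% | 90.0 → 91.9 | 70.0 → 78.6 | 96.4 → 97.1 | 88.0 → 90.4 |
| 95% | 80.0 → 83.4 | 50.0 → 75.9 | 96.8 → 97.5 | 78.5 → 82.8 |
| 95% | 90.0 → 91.9 | 70.0 → 81.8 | 98.3 → 98.6 | 89.0 → 91.2 |

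At q = 5% the smallest rises are 0.5 points in sensitivity (90.0 to 90.5), 2.3 in specificity (70.0 to 72.3), 0.1 in PPV (98.3 to 98.4) and 0.6 in agreement (88.0 to 88.6). Over q = 5 to 20% the ranges are therefore about 0.5 to 3.5, 2 to 26, 0.1 to 1.3 and 0.6 to 4.6 points. Specificity moves most because few operated children lack appendicitis.

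**Step 4: does the direction always hold?** No. Take surgeon error of the same overall rate but unrelated to the read, e = q × (FN + FP). In the example, e = 0.20 × 0.23 = 4.6%. Agreement then falls from 77.0 to 74.5%, specificity from 50.0 to 40.9%, PPV from 93.5 to 89.5% and sensitivity from 80.0 to 79.8%.

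With pathology as the reference (q = 0, tissue result taken as truth), the estimates equal the assumed true values.

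**The case against.** The best reply is that 20.1 does not call intra-operative findings a reference standard. Its sentence could be read as post-operative follow-up confirming what was seen at operation, and pathology is a post-operative result. How pathology enters the final diagnosis is often left to the analysis plan, which is not available here. Part of this stands: the sentence is loose, and an analysis plan might name pathology. But 20.1 does more than stay silent. It names one of two recorded items as what is correlated with the read and leaves out the stronger one. An analysis plan that follows 20.1 would inherit that choice, and one that does not would need 20.1 changed.

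Several stronger readings are tempting and are not supported:

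- A reader might infer that imaging in general is checked against surgery. Section 20.1 mentions only the gray-scale read.
- A reader might infer that gray scale is certainly flattered. That is the expected direction if the surgeon knows the read and leans toward it; the protocol states neither, and unrelated errors work the other way.
- A reader might infer that the primary result, or the contrast between CEUS and gray scale, is biased. The endpoint in 4.1 rests on the blinded radiologist and names no operative reference. No section sets out an accuracy contrast with surgery as truth.
- A reader might infer that one child must carry two diagnoses, confirmed in 20.1 and a negative appendectomy in 4.1. That follows only if negative appendectomy is taken from pathology, and the protocol does not define it.
- A reader might assume 5 to 15 normal appendices per 100 operations, with 30 to 50% of them called inflamed, and read the resulting 1.5 to 7.5 children as PPV points. That requires all 100 children to be gray-scale positive, and the rates are not in the protocol. The hypothesis in 2.2 concerns inconclusive gray scale, and 6.1 allows for diagnosis through CT.

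**Conclusion.** The point holds in a limited form. Section 20.1 uses the weaker of two recorded sources to check gray scale, leaves pathology without a role, and provides no surgical or pathological check on CEUS. The operative impression is probably not independent of the gray-scale read, so the correlation may favour gray scale.

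The primary endpoint is unaffected. The exposure is in the gray-scale correlation and, depending on the reference they end up using, in the definitive-diagnosis and negative-appendectomy endpoints. The size cannot be derived from the protocol. The illustration shows only that, if surgical calls lean toward the read, PPV would move little and specificity could move a good deal. It rests on assumed prevalence, accuracy and q, and on treating pathology as error-free. The case for change does not depend on which way the error runs, because the better reference is already in the dataset.

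**What to change.** In 20.1, name final pathology (collected under 6.4) as the reference diagnosis for operated children, and apply it to both the gray-scale read and the CEUS read. State that the negative appendectomy rate in 4.1 is derived from the same pathology result. Keep intra-operative findings as a secondary description, and tabulate where they disagree with pathology.

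The cost is slightly more than wording. Checking CEUS against pathology adds an analysis, and defining the group as operated children may differ from those who meet the criteria in 20.1. No new data are needed. Pathology settles the diagnosis only in children who have surgery, so the results should be labelled as applying to that group.

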## 21.0 Provisions to Monitor the Data to Ensure the Safety of Subjects

This study proposes a one-time intervention of CEUS. Subjects will be monitored in real time at the time of and following the CEUS. Data collected will be evaluated after the first 10 subjects are enrolled.

- All data collected on subjects who receive study drug will be analyzed for safety. The proportion of patients with specific adverse events will be reported as well as the worst grade observed across all adverse events. The maximum confidence interval width for these estimates is 16.8%. If the observed estimated adverse event proportion is 10%, the 95% confidence interval is (5.3,15.6%).
- Safety information will be collected at the time of study visit when the patient is monitored during contrast administration.
- Safety data collection will begin with the first participant. Participants will be monitored in real time.
- The PI or an assigned co-investigator will be responsible for monitoring the data.
- Cumulative data will be reviewed on a weekly basis beginning with the first study participant.
- All data collected on subjects who receive study drug will be analyzed for safety. The proportion of patients with specific adverse events will be reported as well as the worst grade observed across all adverse events. The maximum confidence interval width for these estimates is 16.8%. If the observed estimated adverse event proportion is 10%, the 95% confidence interval is (5.3,15.6%).
- Any adverse event resulting from the contrast agent requiring an ICU admission will trigger an immediate suspension of the research.

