## 10.0 Study Timelines

- An individual subject's participation in the study will comprise of one study procedure (contrast enhanced ultrasound will take 10 to 20 minutes total) we anticipate study duration will take approximately 30-60 minutes in length. Additionally data generating from SOC will be obtained from chart.
- Assuming an accrual rate of 15-20 subjects per month, we estimate enrollment will take 12-15 months to enroll 250 subjects.
- The Approximate study end date will be 3 years after IRB approval.

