**13.0 Local Number of Subjects**

*13.1 This study will enroll 250 subjects. Assuming an accrual rate of 15-20 subjects per month, we estimate it will take 12-15 months to complete enrollment.*

*13.2 Based on prior data, approximately 375 children are diagnosed with appendicitis at our institution per year. We plan to screen up to 750 potential subjects for eligibility over the course of the study.*

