## **16.0 Withdrawal of Subjects**

- 16.1 As this study consists of a one-time intervention, we do not anticipate any circumstance in which a subject will be withdrawn without their consent.
- 16.2 Subjects may choose to discontinue study participation at any time, for any reason, specified or unspecified, and without prejudice. Subjects may be discontinued from the study for any of the following reasons:
  - At the subject's or their parent's/LAR's request
  - At the discretion of the site investigator as deemed appropriate for any reason

Procedures for orderly termination will include a discussion with the parents or LAR for the reasons behind early termination.

16.3 If a subject withdraws from the research study, data that has already been collected may still be used; however, no new information will be collected except information related to adverse events or other safety issues.

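### The safety precision figures in section 21 (maximum CI width 16.8%; 5.3% to 15.6% at an observed 10%) do not correspond to the planned 250 subjects

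*Protocol*

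**What the plan says.** Section 21.0 defines the safety population by exposure: "All data collected on subjects who receive study drug will be analyzed for safety". It then gives two precision figures. The first is "The maximum confidence interval width for these estimates is 16.8"%. The second is "If the observed estimated adverse event proportion is 10%, the 95% confidence interval is (5.3,15.6"%). The bullet with these sentences appears twice in the section, with the same figures. Neither occurrence gives the number of subjects or the interval method behind them.

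The only study size in the protocol is 250. The Study Summary lists it as the sample size. Section 13.1 says "This study will enroll 250 subjects", section 20.2 says "Enrollment will consist of up to 250 participants", and section 10.0 says "we estimate enrollment will take 12-15 months to enroll 250 subjects". No dropout rate, evaluable number or smaller safety population is given anywhere.

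**The concern.** The width of a confidence interval for a proportion depends on the number of subjects, the observed proportion, the confidence level and, to a small degree, the method. For 250 subjects the 95% interval is widest at an observed 50%, where it is about 12 to 13 points. The stated 16.8 points is about a third wider than that, too much to be rounding or choice of method, and it points to a much smaller sample.

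The figures are the protocol's quantitative statement of how precisely adverse event rates will be known, in a study giving a contrast agent off-label to children. As printed, a reader cannot tell whether they assume about 140 dosed children or 250. The practical stake is limited. The automatic suspension in section 21.0 is triggered by any contrast-related adverse event that requires ICU admission, and neither the primary endpoint in section 4.1 nor the enrolment target in section 13 refers to these intervals.

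**Working it through.** **Inputs**
- Subjects: 250 (Study Summary; sections 10.0, 13.1 and 20.2).
- Stated maximum width: 16.8 points (section 21.0).
- Stated interval at 10%: 5.3% to 15.6%, so a width of 15.6 − 5.3 = 10.3 points (section 21.0).
- Confidence level: 95% (section 21.0).

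**Formulas**
- Wald: p ± 1.96·√(p(1−p)/n). The width is greatest at p = 0.5.
- Exact (Clopper-Pearson): the lower limit is the 0.025 quantile of Beta(x, n−x+1), and the upper limit is the 0.975 quantile of Beta(x+1, n−x).
- Wilson, Agresti-Coull and Jeffreys in their usual forms.

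**Step 1. Try to reproduce the stated figures at n = 250**

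Wald, maximum width: 2 × 1.96 × √(0.25/250) = 12.4 points. 
Wald, at 10%: 10% ± 1.96 × √(0.09/250) = 10% ± 3.72 points, or 6.28% to 13.72%.

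| Method, n = 250 | Maximum 95% width (points) | 95% CI for 25/250 | Width at 10% (points) |
|---|---|---|---|
| Exact | 12.73 | 6.58% to 14.41% | 7.83 |
| Wald | 12.40 | 6.28% to 13.72% | 7.44 |
| Wilson | 12.30 | 6.87% to 14.35% | 7.48 |
| Agresti-Coull | 12.30 | 6.82% to 14.39% | 7.58 |
| Jeffreys | 12.34 | 6.74% to 14.18% | 7.44 |
| **Protocol** | **16.8** | **5.3% to 15.6%** | **10.3** |

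No method gives either stated figure. Continuity corrections do not help: maximum width is 12.80 (Wald) and 12.70 (Wilson). A different confidence level does not help either. At 99% and n = 250 the maximum width is 16.3 (Wald) or 16.6 (exact), and the text says 95%.

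**Step 2. Find the n that the maximum width implies**

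Inverting Wald: n = (1.96/0.168)² = 136. The values of n at which the maximum width rounds to 16.8 are:
- Exact: 145 to 146
- Wald: 136
- Wilson and Agresti-Coull: 132 to 133
- Jeffreys: 133 to 134

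Across the five methods this is 132 to 146. Relative to 250, (250 − 146)/250 = 42% and (250 − 132)/250 = 47% fewer subjects. The two continuity-corrected methods need 144 (Wilson) and 147 to 148 (Wald).

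**Step 3. Check whether the 10% interval agrees**

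Inverting Wald for a width of 10.3 points at 10%: n = (2 × 1.96)² × 0.09 / 0.103² = 130. Across all seven methods the width implies about 128 to 153 subjects, so both figures point to a similar sample size.

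A search over whole-number counts for an interval rounding to (5.3, 15.6) finds, among the five methods:
- Exact, 14/146 (9.6%): 5.34% to 15.57%, with maximum width 16.76 at n = 146. This matches both stated figures.
- Wald, 14/134 (10.4%): 5.27% to 15.63%, but maximum width 16.93, which rounds to 16.9.
- Jeffreys, 12/126 (9.5%): maximum width 17.29, which does not match.
- Wilson and Agresti-Coull: none.

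The most likely origin is therefore an exact calculation for 146 subjects, with 9.6% rounded to 10%. This is inferred; the protocol does not say so.

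**The case against.** The other side has several fair points.

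- **The dosed number may be below 250.** Section 20.2 sets 250 as a ceiling, and section 21.0 counts only subjects who receive the drug. Permission must be signed before the gray-scale scan (section 25.1), the contrast is given after it (section 6.2), and section 16.2 allows discontinuation for any reason, so some enrolled subjects may never be dosed. Section 16.1 ("we do not anticipate any circumstance in which a subject will be withdrawn without their consent") does not settle this, because it concerns withdrawal and not dosing. This stands as a possibility, but reaching 146 would leave 250 − 146 = 104 of 250 enrolled subjects undosed, and nothing in the protocol plans a loss of that size.
- **16.8% is called a maximum, and at 250 the width is indeed below it.** This stands for the first sentence. It does not rescue the second, which states a specific interval that is wrong at 250 under every method tried.
- **The interval method may be left to the SAP.** Agreed. Its absence is not the fault; the printed numbers are.
- **The reconstruction is post hoc.** Also fair. At exactly 10%, no sample size gives both stated limits: the exact method gives a lower limit of 5.3% at n = 119 to 124 and an upper limit of 15.6% at n = 164 to 168. The match needs 9.6%. But the mismatch at 250 does not depend on knowing where the figures came from.
- **Nothing hangs on the figures.** This stands, and it limits the weight of the point.

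**Conclusion.** The concern holds. The precision figures in section 21.0 do not belong to the planned study of 250. At 250 dosed, the maximum 95% width is 12.3 to 12.7 points and not 16.8, and an observed 10% has an interval 7.4 to 7.8 points wide and not 10.3. The stated maximum width fits 132 to 146 subjects.

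This rests on two assumptions: essentially all 250 planned subjects are dosed, since no smaller number is given, and the interval is one of the standard 95% methods.

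The error understates precision, so it does not overstate what the study would show about safety. It should be corrected because the numbers are wrong as written and leave the assumed number of dosed children unclear. It does not affect the conduct of the study, the suspension trigger or any endpoint.

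**What to change.** In both places in section 21.0, state the denominator and the interval method and replace the figures. For example: if 250 subjects are dosed, the maximum exact (Clopper-Pearson) 95% CI width is 12.7%, and for an observed 10% (25/250) the exact 95% CI is 6.6% to 14.4%.

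If fewer dosed subjects are expected, state that number, say why it is below 250, and compute the figures for it. As an illustration, 200 dosed gives a maximum exact width of 14.3%, and 20/200 gives 6.2% to 15.0%. The repeated bullet could be deleted, so that only one set of figures has to be maintained.

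The cost is two sentences of protocol text in two places, with no operational change.

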## 17.0 Risks to Subjects

17.1 As part of SOC, all patients enrolling in this study will have at least one functioning intravenous catheter placed during the SOC blood draw, hence no new IV access will be required. We expect that there may be some mild discomfort related to the performance of the ultrasound study itself and will monitor for this. Other than the discomfort from the ultrasound probe, we do not expect any other ultrasound-related discomfort. Patients will be monitored by licensed personnel during the study interval. Per standard of care, patients will return to the ED while the results of their gray scale ultrasound and CT, if one was taken, are obtained. ED staff will continue to monitor patients for any adverse event.

Reported risks related to Lumason administration include:

Adverse Reaction	Number	(%)
Any Adverse Reaction	340	5
Headache	65	1
Nausea	37	0.5
Dysgeusia	29	0.4
Injection site pain	23	0.3
Feeling hot	18	0.3
Chest discomfort	17	0.2
Chest pain	12	0.2
Dizziness	11	0.2
Injection site warmth	11	0.2

Serious cardiopulmonary reactions, including fatalities, have occurred uncommonly in adults during or shortly following administration of ultrasound contrast agents, including Lumason. These reactions typically occurred within 30 minutes of administration. Hypersensitivity reactions such as skin erythema, rash, urticaria, flushing, throat tightness, dyspnea, or anaphylactic shock have uncommonly been observed following the injection of Lumason. The exclusion criteria eliminate any subjects with a known cardiac abnormality or a known sensitivity to sulfur hexafluoride, so we do not anticipate that these reactions will occur. Resuscitation personnel and equipment will be available during the study treatment and follow-up period.

17.2 This study poses a minor increase over minimal risk as Lumason will be used off-label, but the intervention presents an experience that is reasonably commensurate with those inherent to the subject's medical situation. The only risks attributable to the study are those

of the adverse reactions listed above, as these patients will have already had an IV placed, and would have ultrasound as part of their appendicitis workup. Furthermore, Lumason is currently FDA approved, and in use at CMH, for other abdominal CEUS applications such liver lesions and vesicoureteral reflux in pediatrics.

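### Section 21 ties safety data to contrast administration, and the 6.4 symptom list leaves out most hypersensitivity reactions named in 17.1, so later or unlisted reactions may be missed

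*Protocol*

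**What the plan says.** Protocol section 21.0 states when safety data are gathered: "Safety information will be collected at the time of study visit when the patient is monitored during contrast administration". The same section describes a wider period of observation: "Subjects will be monitored in real time at the time of and following the CEUS". Two other places extend it beyond radiology. Section 6.3 says "ED/ floor staff will continue to monitor patients for any adverse events", and section 17.1 says "ED staff will continue to monitor patients for any adverse event". Neither gives an end time.

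On timing of risk, section 17.1 says "Serious cardiopulmonary reactions, including fatalities, have occurred uncommonly in adults" and adds: "These reactions typically occurred within 30 minutes of administration". It then names seven hypersensitivity reactions as uncommon. Section 10.0 says the "contrast enhanced ultrasound will take 10 to 20 minutes total" and puts study duration at about 30 to 60 minutes.

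On content, section 6.4 says: "Reports of headache, nausea, altered taste, injection site reaction, feeling hot/ flushed, chest pain, or dizziness will also be recorded". The data points there also include a field for other findings or comments.

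For analysis, section 21.0 promises the proportion of patients with each specific adverse event and the worst grade across all adverse events, among everyone who receives the agent.

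**The concern.** The protocol watches children for longer than it says it records them. The only sentence that fixes the timing of safety data attaches it to contrast administration. No sentence says how an event first seen by ED or floor staff becomes a safety record, or when recording ends. The symptom list also follows the common, mild reactions in the 17.1 table and gives no named field to most of the hypersensitivity reactions in the text below that table.

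What is at stake is the numerator of the adverse-event proportions. An event that is seen but not recorded cannot be recovered by any later analysis plan. The worst-grade summary is exposed too, because the unlisted reactions include some that could set it. Section 17.2 describes the use as off-label, in children, so the safety summary is one of the results readers will look for.

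**Working it through.** **The plan's own figures.** Section 21.0 gives a maximum 95% interval width of 16.8% and an interval of 5.3% to 15.6% at an observed 10%. They describe precision, not capture.
- Wald at n = 250: maximum width = 2 × 1.96 × √(0.25/250) = 12.4%. At 10%: 0.10 ± 1.96 × √(0.09/250) = 6.3% to 13.7%.
- Clopper-Pearson at n = 250: maximum width 12.7%, and 25/250 gives 6.6% to 14.4%.
- The printed figures fit about 146 subjects by Clopper-Pearson (maximum width 16.76%; 14/146 gives 5.3% to 15.6%).

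They therefore do not match the planned 250. That is a separate matter and does not affect this point.

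**Step 1: the windows side by side.**

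| Element | Period | Source |
|---|---|---|
| Safety data collected | Study visit, while monitored during contrast administration | 21.0 |
| Real-time monitoring | During and after CEUS | 21.0 |
| ED/floor monitoring | After leaving radiology, no end time | 6.3, 17.1 |
| Serious cardiopulmonary reactions (adults) | Typically within 30 minutes of administration | 17.1 |
| CEUS | 10 to 20 minutes | 10.0 |
| Study duration | About 30 to 60 minutes | 10.0 |

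Suppose recording stopped when the CEUS ended. The 30 minutes run from administration, which takes place within the CEUS. At least 30 − 20 = 10 minutes would then remain after a 20-minute examination, and at least 30 − 10 = 20 minutes after a 10-minute one. Under the broader reading, where recording covers the whole visit, the interval might be covered. The protocol does not say how much of the 30 to 60 minutes falls after injection.

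**Step 2: the reactions side by side.**

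| Named in 17.1 | On the 6.4 list? |
|---|---|
| Headache, nausea, dysgeusia, dizziness | Yes |
| Injection site pain, injection site warmth | Yes, as injection site reaction |
| Feeling hot; flushing | Yes |
| Chest pain, chest discomfort | Chest pain only |
| Rash, urticaria, skin erythema | No |
| Dyspnea, throat tightness | No |
| Anaphylactic shock | No |
| Serious cardiopulmonary reactions | No named item; chest pain is the nearest |

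Of the seven hypersensitivity reactions named in 17.1, one (flushing) is listed and six are not.

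**Step 3: direction and size.** If the true proportion of affected children is p and a share c of them is recorded, the expected observed proportion is p × c. Because c cannot exceed 1, missed events can only lower the result. The documents give no onset distribution for these reactions and no share that falls outside the list, so c is unknown and no size follows.

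**The case against.** The strongest reply is that chart review already provides a route. Section 6.4 opens with extraction from the electronic medical record, and its symptom sentence has no time limit. Section 10.0 takes standard-of-care data from the chart. Sections 20.3, 20.5 and 20.6 have every chart reviewed by research staff, and 22.3 has the team collect pertinent data from clinical care. Section 16.3 continues to collect adverse-event information even after withdrawal. Section 23.1 sends adverse events to the principal investigator and the IRB, and section 21.0 suspends the study after a contrast-related ICU admission. In addition, 6.4 has a comments field, adverse events are not an endpoint in 4.1, and detailed fields may sit in case report forms that are not shown.

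Much of this stands, and it rules out three stronger readings.

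- A reader might infer that safety is recorded *only* while contrast is given. Section 21.0 does not say only, it refers to the study visit, and the protocol provides for later monitoring.
- A reader might infer that the list omits hypersensitivity and cardiopulmonary reactions altogether. Chest pain and feeling hot or flushed are on it, and nothing declares it exhaustive.
- A reader might infer that the proportion *will* be understated, and compute by how much by spreading the 5% any-reaction figure in 17.1 evenly over 30 minutes. The 30 minutes are given for serious cardiopulmonary reactions in adults, with the word typically. They are not given for headache or nausea, nor as an upper limit, and nothing supports uniform onset.

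The reply does not close the gap. None of the chart-review sentences names post-contrast adverse events. Reporting to the IRB and an ICU stop make it unlikely that the gravest events go unseen, but they do not place a late rash or dyspnea in the analysed data. A free-text field is a weak basis for proportions by event.

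**Conclusion.** The point holds as an inconsistency within the protocol that should be reconciled. The stated collection period is narrower than the stated monitoring and can end before the interval that 17.1 names. The stated symptom list does not cover the risks in 17.1 or the all-event summary in section 21.0. Followed as written, these rules may lose later or unlisted reactions, and the adverse-event proportions and worst grade may be biased low.

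The direction rests only on the fact that unrecorded events reduce the numerator. The size cannot be derived from the document, and none is claimed. Whether any loss occurs depends on how staff apply the section 21.0 sentence and how fully they use chart review and the comments field. This is a cheap improvement to the safety data and does not bear on the primary endpoint.

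**What to change.** These changes affect data capture only and alter no clinical care.

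1. Reconcile the collection sentence in section 21.0 with the monitoring described in 6.3, 17.1 and 21.0. Adverse-event recording should run from injection through the post-CEUS monitoring period, with a stated end that covers at least the interval named in 17.1.
2. Name the ED or floor chart as a source of adverse-event data.
3. Add to the 6.4 list the reactions that 17.1 names and 6.4 lacks: skin erythema, rash, urticaria, throat tightness, dyspnea, anaphylactic shock and serious cardiopulmonary reactions.

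The cost is a few more REDCap fields and some chart abstraction for each child. The reported adverse-event rate may come out slightly higher.
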